In Aim 2, at least 50 primary care team members will be recruited to participate in a virtual six-month TB infection ECHO course. Participants will complete quantitative surveys before and after the course as well as post-session surveys following each session. Survey questions will assess feasibility measures related to process, resources, and management and impact measures related to learning and performance. Paired data from pre- and post-course surveys will be analyzed accordingly depending on the distribution of results. The nature of this pilot project provides budgetary limits for an effective sample size. Therefore, for analyzed question responses that do not demonstrate a significant change between pre- and post- we will carefully note any relevant trends. In addition to the quantitative survey results, we will conduct approximately 15 qualitative interviews with ECHO participants. Given that practice change is difficult to assess quantitatively, questions will be asked regarding the impact of the ECHO course on practice change and about improvements that can be made to future LTBI ECHO courses.

Specific Aim 3: Pilot a retrospective electronic medical record (EMR) data review to examine RI PCPs' testing and treatment before and after ECHO implementation and evaluate the model's reach.

In Aim 3, data will be retrospectively extracted from two participants' clinics to research RI PCPs' testing and treatment patterns before and after the ECHO course. Aim 3 will evaluate the model's reach, or the degree to which the population that is eligible to benefit from an intervention actually benefits. In the case of LTBI, there is one lab test type (interferon gamma release assay) and two medications (rifampin and isoniazid) used. They are used sparingly for other ailments in primary care. Therefore, LTBI lab tests and prescriptions could be an excellent proxy measure of providers' behavior change related to LTBI testing and treatment, and ultimately the reach of the ECHO model.

B. Background

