Tuberculosis (TB) remains a significant cause of mortality globally.¹ In the United States (US), 80% of TB disease is a result of untreated, latent TB infection. This persists despite available treatment that can significantly decrease the rate of progression from TB infection to disease.² Currently, up to 13 million individuals have latent TB infection in the US, and approximately 10% of these individuals will progress to infectious TB disease.³ In 2016, the United States Preventive Services Task Force (USPSTF) updated their latent TB infection recommendation to a Grade B based on strong evidence supporting TB infection testing and treatment as a preventive measure, signifying its importance.⁴

Accordingly, the USPSTF recommendation encourages primary care providers (PCPs) to add TB testing to their routine preventive screening and initiate treatment in the primary care setting – tasks that were previously reserved for specialists. Unfortunately, primary care training incorporates only minimal training regarding TB, and therefore, PCPs in the US are not prepared to incorporate testing and treatment for this critically under-addressed infection. Due to this significant gap in training, PCPs continue to refer patients to specialists for treatment. These unnecessary referrals are likely to complicate care for patients, resulting in barriers to initiation and completion of TB infection therapy and, ultimately, increased healthcare costs.

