We will use purposive sampling for the recruitment of both qualitative interview participants and ECHO course participants. In our alumni and community provider network at Brown Family Medicine and Care New England, there are many female and male primary care team members. Given our small sample of at least 40 key informant interviews and at least 50 participants for the TB infection ECHO, we do not anticipate any challenges in recruiting an equal number of men and women.

Regarding minorities, our primary care network has < 10% minority primary care providers. Using purposive sampling, we will make every effort to ensure that our sample includes 10% or more minorities to represent the general PCP population in RI.

E Study Design

Exploratory Sequential Translational Research Design Overview: Primary care team member KAS gaps are suspected barriers that impact all steps of the LTBI care cascade yet they have not been formally studied in the literature. This study will utilize a four-phase exploratory sequential mixed methods design²³, in which we will: 1) Explore these TB infection KAS gaps qualitatively (Aim 1), 2) Translate the qualitative findings to inform curriculum design within an innovative, evidence-based telementoring model, and inform quantitative surveys that measure key implementation outcomes (Aim 2), and 3) Implement a LTBI ECHO intervention for RI primary care teams and utilize the survey instrument as well as qualitative interview feedback to assess *feasibility* and *impact* of the LTBI ECHO intervention (Aim 2), and 4) Pilot a retrospective EMR review to assess the reach of the LTBI Echo on patients' care.

Qualitative Methods

In the first phase of this four-phase exploratory sequential translational research study, we will use qualitative key informant interviews to explore, for the first time, the potential gaps listed above that impact latent TB infection testing and treatment.

Key Informant Interviews (KII): In collaboration with the RI Department of Health, we will identify a purposive sample of key informants from our Brown Department of Family Medicine and Care New England networks of primary care provider teams practicing outpatient primary care and serving immigrant populations. In total, there will be at least 40 KIIs. Interviews will be conducted to the point of data saturation such that no new information is obtained, adding more KIIs if needed.

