Instrument Development and Interview Structure: With mentorship from [name], a semi-structured question guide for the KIIs will be developed based on the knowledge, attitudinal, and skill gaps in Table 1. The semi-structured guide will include open-ended core questions that will be supplemented with spontaneous probes and follow-up questions to explore the possible barriers impacting all latent TB infection steps.

The ECHO Model

The ECHO Model uses a virtual hub-and-spoke educational approach to successfully link interdisciplinary expertise to generalists to increase their ability to manage complex medical cases and ultimately address growing public health problems.¹⁰ Unlike “telemedicine” where specialists assume care of the patient, the ECHO model allow generalist clinicians to retain responsibility for managing patients. Participants from similar settings with similar barriers learn from each other through shared case management discussion and decision-making. The ECHO model typically consists of a fifteen-minute didactic presentation by a content expert followed by

case-based discussions of one or two de-identified latent TB infection cases presented by participants. Cases are prepared and submitted prior to each ECHO session using an ECHO case presentation form. Cases are reviewed by ECHO leads (in our case, these will be reviewed by the PI and [name]) to ensure adequate data are included for discussion. As part of the ECHO model, descriptive data for each session (date, topic, length, case presentations, participant demographic information) are collected through 'iECHO' and accessible to hub members at any time through a web-based, password protected platform.

A *TB infection ECHO educational intervention* will be designed that specifically addresses the KAS gaps identified in Aim 1 so that the course content is specific to Rhode Island primary care team members .

Participant Recruitment: A random and representative sample of at least 40 primary care team members will be purposively recruited. Gender, race, and practice setting during recruitment will be considered to enhance the diversity of our sample. However, given the two-year time frame, it may not be possible to achieve equal demographics for our participant sample. Participants who attend at least four out of six latent TB infection ECHO sessions will receive CME credits.

Quantitative Methods

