Potential variables related to testing and treatment will be discussed with the health centers or clinic sites, and data extraction will be requested through the site's data team. Data variables to be queried will include provider ECHO enrollment, HIPAA compliant patient demographic information, ICD-10 diagnosis code to separate TB disease from TB infection, TB infection laboratory testing data, and LTBI prescriptions. At Blackstone Valley Community Health Center, the following additional information will be included in the database: age, gender, primary language, country of origin, refugee status if available, ICD-10 diagnoses to separate TB disease from TB infection, date of IGRA test, type of IGRA test, IGRA test result, LTBI evaluation including chest x-ray and documentation of symptom screen, LTBI treatment plan including referral and/or LTBI treatment initiation (medications such as rifampin or isoniazid), and treatment completion or documentation from specialist of LTBI treatment completion. Data will be retrospectively collected to capture the three months prior to LTBI ECHO implementation, six months during the LTBI ECHO, and three months after LTBI ECHO implementation. We will work with health center sites to determine the best way to link ECHO participants to health center data. This could include health centers including provider names in the database if acceptable or providing health centers with names of their ECHO provider participants and having them code the database in a way that enables the study team to differentiate ECHO participants from other providers and protect anonymity. [name] in her role as co-investigator will oversee the ECHO participant linkage with health center data.

G Data Analysis

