For the impact analysis, the majority of these questions will be likert-scale type. The distributional properties of the pre- and post- responses will be examined. The paired data will be analyzed using Wilcoxon-signed rank test or a paired t-test depending on whether or not the responses seem to be following a normal distribution. Significance will be considered if *p-value* is < 0.05 .

Regarding Aim 3, Blackstone Valley Community Health Center has been selected as one of our sites. Currently, BVCHC staff are reviewing patient charts for clinical purposes in order to design a latent TB infection clinic. Therefore, a de-identified database with LTBI tests ordered and LTBI prescriptions written by PCPs exists. For the purpose of this study and after written approval from BVCHC, this de-identified patient database will be provided to the study team as per the data sharing agreement. Once we identify another site, data variables from the two EMRs will be sorted, matched, and coded synchronously so that all data can be analyzed together. We will work with health center sites to determine the best way to link ECHO participants to health center data. Descriptive statistics will be performed to determine the number of LTBI tests ordered and LTBI treatment prescribed by PCPs in each time period (before, during, after). We will study potential denominators including total number of patient visits, number of wellness visits, number of patients diagnosed with LTBI, and number of visits with immigrant/refugee patients to explore the best potential measures of effectiveness in future studies. Comparison between the ECHO participants and non- ECHO participants will also be considered to assess initial trends.

H. Material Inducements

Knowledge gained.

I. Training of Research Personnel

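### Aim 3's only treatment measure counts PCP prescriptions, so as a measure of patient reach it cannot separate a change of prescriber from additional patients treated

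*Combined protocol and SAP*

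**What the plan says.** - **What reach means.** Section 2.A (Specific Aim 3) defines it as "the degree to which the population that is eligible to benefit from an intervention actually benefits". The design overview in section 2.E says the EMR review will "assess the reach of the LTBI Echo on patients' care".
- **The proxy.** Section 2.A offers it with a hedge: "LTBI lab tests and prescriptions could be an excellent proxy measure of providers' behavior change", and ultimately of reach.
- **The analysis.** Section 2.G will determine "the number of LTBI tests ordered and LTBI treatment prescribed by PCPs in each time period". No other treatment measure is named for Aim 3. Four possible denominators will be explored: all visits, wellness visits, LTBI diagnoses, and visits by immigrant or refugee patients. A comparison of ECHO participants with other providers will be considered.
- **Care before the course.** Section 2.B says "PCPs continue to refer patients to specialists for treatment".
- **Intended mechanism.** Section 2.E says "the ECHO model allow generalist clinicians to retain responsibility for managing patients".
- **Data.** In section 2.F, the general variable list ends with "TB infection laboratory testing data, and LTBI prescriptions" and has no referral item. For Blackstone Valley Community Health Center (BVCHC) only, the additional items include "LTBI treatment plan including referral and/or LTBI treatment initiation (medications such as rifampin or isoniazid" and, later in the same list, completion of treatment or a specialist's record of it. Section 2.G gives none of these extra items a role.

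**The concern.** The treatment route left out of the count is the one that the course is meant to shrink. A patient referred and treated by a specialist before the course adds nothing to the PCP count. A similar patient treated by the PCP afterwards adds one. The count then rises although the number of patients treated has not changed.

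For provider behaviour this is no fault, because the prescriber has changed and the count shows it. The difficulty comes when the same rise is reported as reach on patients. The reader cannot tell how much of it is treatment moved between settings and how much is patients who would otherwise have gone untreated. Section 2.G also uses this pilot to look for effectiveness measures for later studies, so the distinction should be visible in the pilot's own tables.

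**Working it through.** The plan has no figure to reproduce: Aim 3 is descriptive and gives no expected counts, referral share or treatment rates. The check is simple accounting, and every input below is an assumption.

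**Inputs (assumed).** 100 LTBI-diagnosed patients in each of two equal-length periods (the before and after windows in section 2.F are three months each). *s* is the share managed by the PCP, the rest being referred. *p* is the probability of treatment if PCP-managed, and *r* the probability if referred.

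**Formulas.**
- PCP count = 100 × s × p
- Treated by any route = 100 × [s × p + (1 − s) × r]

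**Main case: p = 0.60, s from 0.30 to 0.60.**
- PCP count before: 100 × 0.30 × 0.60 = 18
- PCP count after: 100 × 0.60 × 0.60 = 36, a rise of 100%

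| r (assumed) | Any route, before | Any route, after | Change |
|---|---|---|---|
| 0.60 | 18 + 70 × 0.60 = 60 | 36 + 40 × 0.60 = 60 | 0% |
| 0.45 | 18 + 70 × 0.45 = 49.5 | 36 + 40 × 0.45 = 54 | +9% |
| 0.30 | 18 + 70 × 0.30 = 39 | 36 + 40 × 0.30 = 48 | +23% |
| 0.70 | 18 + 70 × 0.70 = 67 | 36 + 40 × 0.70 = 64 | -4% |

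The PCP count doubles in every row. The any-route total stays flat, rises modestly or falls slightly.

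**Other shifts in s, with the same p and the same four values of r.** For 0.2 to 0.3, 0.5 to 0.8 and 0.8 to 0.9, the PCP count rises by 50%, 60% and about 12%. The any-route change lies between -5% and +20%.

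**Do the planned denominators help?** Per LTBI-diagnosed patient, the PCP measure goes from 18/100 = 0.18 to 36/100 = 0.36, which is still a doubling. The three visit-based denominators also leave the numerator as it is.

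**Does the comparison with other providers help?** No. If participants refer less after the course than their colleagues do, the change of prescriber appears as a difference in their favour.

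**Would adding PCP starts to specialist completions help?** Only in part. Let *c* be the fraction of specialist-treated patients with documented completion. With p = r = 0.60, the sum goes from 18 + 42c to 36 + 24c, a difference of 18 × (1 − c). That is positive whenever c is below 1, although the number of patients starting treatment is 60 in both periods. The two routes must be counted at the same event.

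**The case against.** The strongest reply is that moving treatment into primary care is itself the benefit. Section 2.B calls the referrals unnecessary and links them to barriers to starting and finishing therapy, and the stated purpose of ECHO is to widen access to care once confined to specialists. On that view, a patient treated by a specialist before the course was not reached by ECHO, and a patient treated by the PCP afterwards was. This stands in part: the PCP count is a fair measure of treatment moved into primary care. But the protocol's own complaint about referral is that fewer patients start and complete treatment, and whether that improves can be seen only when both routes are shown.

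Several other points also stand. The proxy is hedged and includes tests ordered, which a change of prescriber does not affect. Aim 3 has no hypothesis test. Section 3.C allows further variables to be added, and referral is on the BVCHC list, so its use is unspecified and not ruled out.

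Three stronger readings are tempting, and the documents do not support them:
- A reader might infer that the plan will report a higher PCP count as more patients treated. Section 2.G labels the count by prescriber and does not say this.
- A reader might infer that PCP prescriptions say nothing about reach. The definition in section 2.A leaves open whether care moved into primary care counts as benefiting.
- A reader might infer that BVCHC already holds the referral data. Section 2.F says those items are to be included; section 2.G describes the existing database as holding tests and PCP prescriptions.

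**Conclusion.** The point holds as a limit on interpretation. As planned, a rise in PCP-prescribed treatment cannot be divided between a change of prescriber and additional patients treated, and neither the denominators nor the comparison with other providers resolves this. The count remains valid for provider behaviour, and tests ordered are untouched.

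The size at these sites cannot be derived from the documents. The doubling against a change of -4% to +23% shows how far the two measures can part under assumed rates; it is not an estimate for Rhode Island. If referral does lose patients, as the Background suggests, part of any rise is real. In the assumed case with r = 0.30, that part is 23% against 100% for the PCP count.

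No p-value or sample size is affected. The gain is a clearer conclusion from a descriptive pilot.

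**What to change.** In section 2.G:

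1. Keep the PCP treatment count and name it as the provider-behaviour measure.
2. Add, by period and per LTBI-positive patient, four shares: PCP treatment started; referred with specialist treatment documented; referred with outcome unknown; neither started nor referred.
3. Do not add PCP starts to specialist completions. Compare the routes on the same event, start with start or completion with completion. Give the any-route total as a range, with outcome-unknown referrals counted first as untreated and then as treated.
4. Use the referral and specialist-documentation items that section 2.F plans for BVCHC, and request the same items in the second site's query.
5. Where a site can supply only PCP prescriptions, word its result as a change in PCP prescribing, not as patient reach.

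**Cost.** A short addition to the analysis text and one or two more fields at a second site that is not yet identified, so its query can still be specified. Specialist documentation will be incomplete, so an unknown category will remain and the range may be wide. If BVCHC's records capture specialist completions but not starts, only the completion comparison will be possible there.

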Specific Aim 2: In this aim, participants will be recruited to participate in the TB infection ECHO course. The same recruitment procedure will be used as in Aim 1 to recruit at least 50 participants. Participants will be invited to complete the survey via email and will complete online consent prior to initiating the survey. Participants who did not complete the quantitative surveys, but volunteer to participate in qualitative interviews will undergo consent virtually prior to the start of the interview.. This study aims to assess the TB infection ECHO course in a real-world setting. Therefore, we will not make any additional efforts to retain participants in the course outside of routine course email reminders.

Specific Aim 3: In this aim, two health centers or clinics with participants who enrolled in the Rhode Island LTBI ECHO will be selected. One of these sites will be Blackstone Valley Community Health Center where the staff is conducting a clinical chart review for latent TB infection. [name], a family medicine physician and public health student, has been added as a co-investigator to assist in the analysis of the de-identified patient database. Further information

about the second site will be provided to the IRB. We will pilot the extraction of electronic medical record data from these two sites. The PI has significant experience with data queries in EPIC at the Family Care Center and has confirmed that prescription data can be queried from this system. The Brown Department of Family Medicine has a strong relationship with health centers and primary care sites throughout Rhode Island. Further, the Center for Primary Care and Prevention has active projects involving data query from EMRS at other clinic sites.

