[name], a medical student, will serve as our research assistant for this study. He will receive qualitative training from [name] and [name] via online lectures and recordings as he will attend the ECHO immersion training and will also assist [name] with the qualitative interviews. Our study team will provide him with any necessary research training to ensure that he can conduct his duties as the research assistant. [name] is a family medicine physician and global health fellow at the Department of Family Medicine at Brown University. She is currently receiving a Masters in Global Public Health at Brown University School of Public Health. We will ensure that her CITI training is up to date and that she receives training and mentorship in quantitative data analysis.

3) Human Subjects

A. Subject Population

For both the qualitative key informant interviews and the quantitative surveys, the eligibility criteria will be the same. Participants must be:

Primary care team members in Rhode Island: This includes MD, DO, nurse practitioners, physician assistants, nurses or other team members who work in a primary care setting. We will exclude individuals who work in urgent care as they do not routinely perform preventive screening such as TB infection screening. Individuals must be able to speak English as interviews and ECHO course will be in English.

There will be no age limits for recruited participants. However, given our training inclusion criteria, all participants will be over the age of 18 since a higher level of training after high school is required for all eligible participants. Therefore, children will not be eligible to participate in this study.

We will use purposive sampling for the recruitment of both qualitative interview participants and ECHO course participants. In our alumni and community provider network at Brown Family Medicine and Care New England, there are many female and male primary care team members. Given our small sample of at least 40 informant interviews and 40-50 participants for the TB infection ECHO, we do not anticipate any challenges in recruiting an equal number of men and women.

Regarding minorities, our primary care network has < 10% minority primary care providers. Using purposive sampling, we will make every effort to ensure that our sample includes 10% or more minorities to represent the general PCP population in RI.

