The retrospective chart review will involve data from ECHO participants as well as data from other providers who have ordered a TB test or prescribed LTBI medication at the two health care centers or clinics that are selected.

B. Recruitment and Consent Procedures

Specific Aim 1: In this aim, at least 40 key informant interviews with primary care team members in Rhode Island will be performed. The department of Family Medicine has a list of all primary care providers who are alumni or are community preceptors. There is also a list of primary care providers including other specialties like internal medicine and pediatrics throughout Care New England. Using these contact lists, participants will be recruited via email initially. Several chief medical officers at federally qualified health centers have given us permission to also circulate recruitment emails via health center listserves to recruit their primary care team members. For those who do not respond positively or negatively, a phone call to their primary care office during business hours will be made. If the participant agrees to be interviewed, a convenient time will be arranged to meet with the participant. Interviews will be performed in a quiet, private location either at the participant's office or in the department of Family Medicine at [name]. Given primary care team members' busy schedules, interviews may also be conducted via phone. In this case, informed consent documents will be sent via the participant's preferred method, email or mail. The consent will be read aloud over the phone, and the verbal consent will be documented by the study team by signing the informed consent and writing a note that informed consent was obtained over the phone for the participant. We will attempt to reschedule interviews up to three times for participants in order to retain them in the interview process.

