Specific Aim 2: In this aim, participants will be recruited to participate in the TB infection ECHO course. The same recruitment procedure will be used in Aim 1 to recruit participants for the ECHO course. Since all registration for the ECHO course is being conducted electronically, an informed consent form will be included at the beginning of the online survey. Participants will confirm their understanding of the consent form and will be provided an email address to send any comments or concerns prior to participation. If an individual does not agree to participate, they will not be able to proceed to the survey. Study participants names will be linked to surveys to allow for possible clinical outcome tracking in Aim 3. Study participants will provide unique IDs so that names will only be included on a codesheet (see below). Only de-identified data with unique IDs will be included in the final database. This study aims to assess the TB infection ECHO course in a real-world setting. Therefore, we will not make any additional efforts to retain participants in the course outside of routine course email reminders. We will email ECHO participants at the end of the course to ask for volunteers to participate in qualitative interviews. Those who agree will undergo the same consent process as described in Aim 1.

Specific Aim 3: The retrospective chart review will be requested through the data teams of the two selected sites and will be de-identified to not include HIPAA protected information.

C. Potential Risks

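### Post-course interviewees are recruited by an open call for volunteers with no selection step, so their accounts may over-represent engaged participants

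*Combined protocol and SAP*

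**What the plan says.** Sections 2.D (Brief Description of Subjects) and 3.A (Subject Population) carry the same general statement: "We will use purposive sampling for the recruitment of both qualitative interview participants and ECHO course participants". In 3.A the sample sizes that follow it are these: "Given our small sample of at least 40 informant interviews and 40-50 participants for the TB infection ECHO". The roughly 15 post-course interviews are not named there.

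For those interviews, section 3.B (Recruitment and Consent Procedures, Aim 2) gives the procedure: "We will email ECHO participants at the end of the course to ask for volunteers to participate in qualitative interviews". The next sentence links back to Aim 1 on consent only: "Those who agree will undergo the same consent process as described in Aim 1". Section 2.F also speaks of volunteering and widens who may be interviewed: "Participants who did not complete the quantitative surveys, but volunteer to participate in qualitative interviews will undergo consent virtually".

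On purpose, section 2.A (Aim 2) says: "Given that practice change is difficult to assess quantitatively, questions will be asked regarding the impact of the ECHO course on practice change". It adds that the interviews will also ask what to improve in future courses. Section 2.E describes the interviews as a supplement to the quantitative survey.

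**The concern.** A purposive sample is chosen by stated characteristics so that the relevant range of experience is covered. An open call at the end of a six-month course leaves that choice to the participants. Those who stopped attending may know most about the barriers, and they are plausibly the least likely to answer a course email by then.

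What is at stake is the content of two sets of themes: whether and how practice changed, and what should be improved. If mostly engaged participants come forward, both may lean favourable, and the reasons for drop-out may be thinly covered. The other feasibility data in sections 2.E and 2.G (attendance, retention and survey proportions) show how many left but give little on why. People who left may also skip the post-course survey.

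**Working it through.** The plan gives no figure for this point, so there is none to reproduce. The check is a comparison of the texts, followed by an illustration.

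**Comparison of Aim 1 interviews with post-course interviews**

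| Element | Aim 1 interviews | Post-course interviews |
|---|---|---|
| Number | at least 40, to saturation (2.E) | about 15 (2.A, 2.E) |
| Selection | purposive sample of key informants from teams serving immigrant populations (2.E) | none described; call for volunteers (3.B) |
| Non-responders | "For those who do not respond positively or negatively, a phone call to their primary care office during business hours will be made" (2.F, 3.B) | none described |
| Carried over from Aim 1 | n/a | consent process (3.B), interview-guide process (2.E) |

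The course itself adds nothing that would keep weaker attenders in contact: "we will not make any additional efforts to retain participants in the course outside of routine course email reminders" (2.F, 3.B).

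**Fraction interviewed**

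The course size is given as at least 50 (2.A), at least 40 (2.E) and 40-50 (3.A). So 15/50 = 30%, or 15/40 = 37.5%. Between 62.5% and 70% of participants would not be interviewed, which makes it matter who is.

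**Illustration of the mix of interviewees**

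The inputs are assumptions and do not come from the documents. Let a be the share of participants attending at least four of six sessions, and k the ratio of their chance of volunteering to that of the others. The four-of-six cut is the protocol's own CME threshold.

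Expected share of high attenders among volunteers = a·k / (a·k + (1 − a)).

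With a = 0.60 and 15 interviews:

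| k | Share | High attenders | Low attenders |
|---|---|---|---|
| 1 | 0.60/1.00 = 60% | 9.0 | 6.0 |
| 2 | 1.20/1.60 = 75% | 11.3 | 3.8 |
| 3 | 1.80/2.20 = 82% | 12.3 | 2.7 |
| 5 | 3.00/3.40 = 88% | 13.2 | 1.8 |

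Rounded, high attenders are 9, 11, 12 or 13 of 15.

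Varying a at k = 3:
- a = 0.40: 1.20/1.80 = 67%, so 10 high and 5 low attenders.
- a = 0.80: 2.40/2.60 = 92%, so about 14 high and 1 low.

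With k = 1 there is no distortion. The plan has no step that would show which k applied. The table describes who is interviewed. It does not measure how far the themes would shift, and no rate is to be estimated from these interviews.

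**The case against.** The strongest reply has four parts.

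1. *The interviews are not the main evidence on practice change.* A reader might infer that they are from the remark in 2.A that practice change is hard to measure quantitatively. The documents do not support that. Section 2.E calls the interviews a supplement, the survey has its own items on numbers tested and treated, and Aim 3 adds EMR counts before, during and after the course, which 2.A regards as a potentially excellent proxy for behaviour change. This part stands. The EMR work, however, is a descriptive pilot at two clinics and cannot explain why practice did or did not change.

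2. *The sections do not flatly contradict each other.* A reader might take the purposive statement as a broken promise. The paragraph goes on to name only the Aim 1 interviews and the course sample, and volunteers could still be selected purposively after they reply. This stands in part. The opening sentence is general, section 3.C speaks of key informant interviews in both Aims 1 and 2, and no later selection step is described. On either reading the post-course interviews have no stated sampling plan beyond self-selection.

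3. *It is not established that only engaged participants will come forward, or that drop-out reasons will be absent.* The email has no attendance condition and survey non-completers are expressly admitted. Even at k = 5 the illustration leaves about two low attenders. This stands, so the wording has to be that engaged participants may be over-represented. Allowing less engaged people to take part does not ensure that any do.

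4. *For practice change, well-exposed participants are a sensible group to interview.* This also stands. Low attenders matter mainly for barriers and course improvement, so how to divide the places is a judgement for the investigators.

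**Conclusion.** The point holds as a minor design weakness. As written, the roughly 15 post-course interviewees select themselves, with no criteria and no follow-up of non-responders, despite a general statement of purposive sampling. The findings may therefore over-represent engaged participants and give little on reasons for drop-out.

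The size cannot be fixed from the documents. On the assumed 60% attendance, the expected number of low attenders among 15 falls from 6 with equal volunteering to about 4, 3 or 2 when high attenders are 2, 3 or 5 times as likely to volunteer. Both the attendance share and the ratios are assumptions, and the direction of the selection is a plausible inference. In a pilot whose interviews are descriptive and sit beside survey and EMR data, this is worth improving because it is cheap. It does not undermine the study.

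**What to change.** Replace the single open call in section 3.B with purposive invitations drawn from the course attendance list:

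- Stratify by attendance (for example at least four of six sessions versus fewer) and by provider type.
- Hold some of the roughly 15 places for low attenders. The number is the investigators' choice.
- After a refusal or non-response, invite the next person in the same stratum.
- Report how many were invited and how many agreed in each stratum.
- Align sections 2.D, 2.F, 3.A and 3.B so that the sampling method for these interviews is stated once and consistently.

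The information needed is already planned: attendance is a feasibility measure and decides CME credit, iECHO holds session and participant data, and provider type is among the demographics on the pre-course survey. The number of interviews stays the same. The costs are targeted emails in place of one general call, slower recruitment because low attenders may decline more often, and somewhat fewer interviews with highly exposed participants.
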